**Inclusion Criteria:**

- Female and male participants  $\geq 18$  years of age.
- Diagnosed within the previous 6 months with histologically confirmed pancreatic adenocarcinoma stage I to IV.
- Participant provides written informed consent for the study.
- Participant must agree to sample collection and genetic testing using the Invitae Multi-Cancer Panel®.

**Exclusion Criteria:**

- Diagnosed with pancreatic adenocarcinoma more than 6 months before presenting to the clinical site.
- Diagnosed with intraductal papillary mucinous neoplasms, mucinous cystic neoplasms, pancreatic neuroendocrine tumors.

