**Study design:**

This is an observational, cross-sectional study. Prevalence will be determined by testing all consecutive patients with histologic diagnosis of pancreatic adenocarcinoma (PAC) regardless of family history, clinical stage and treatment. In other words, the prevalence will be determined in an unselected patient population. To decrease potential survivorship bias, we will include only patients with PAC within 6 months of diagnosis. Participants will provide informed consent and they will allow access to medical records. Patients' demographics and cancer treatment information will be obtained from questionnaires completed by the participants and/or abstracted from medical records. A clinical geneticist will evaluate all patients, with emphasis on the cancer family history. They will provide a blood sample from peripheral access for DNA analysis; 10 mL of whole blood mixed with EDTA will be collected from each patient. We will use a commercial panel (Invitae Multi-Cancer Panel®) for DNA analyses.

Invitae Multi-Cancer Panel® analyzes 84 genes associated with hereditary cancers, including all genes specifically associated with hereditary pancreatic cancer. Invitae is a College of American Pathologist (CAP)-accredited and Clinical Laboratory Improvement Amendments (CLIA)-certified clinical diagnostic laboratory performing full-gene sequencing and deletion/duplication analysis using next-generation sequencing technology (NGS). The Invitae Multi-Cancer Panel includes 84 genes: *AIP, ALK, APC, ATM, AXIN2, BAP1, BARD1, BLM, BMPR1A, BRCA1, BRCA2, BRIP1, CASR, CDC73, CDH1, CDK4, CDKN1B, CDKN1C, CDKN2A, CEBPA, CHEK2, CTNNA1, DICER1, DIS3L2, EGFR, EPCAM, FH, FLCN, GATA2, GPC3, GREM1, HOXB13, HRAS, KIT, MAX, MEN1, MET, MITF, MLH1, MSH2, MSH3, MSH6, MUTYH, NBN, NF1, NF2, NTHL1, PALB2, PDGFRA, PHOX2B, PMS2, POLD1, POLE, POT1, PRKAR1A, PTCH1, PTEN, RAD50, RAD51C, RAD51D, RB1, RECQL4, RET, RUNX1, SDHA, SDHAF2, SDHB, SDHC, SDHD, SMAD4, SMARCA4, SMARCB1, SMARCE1, STK11, SUFU, TERC, TERT, TMEM127, TP53, TSC1, TSC2, VHL, WRN, WT1*. Genes are tested for punctual variations in the sequence and for deletion/duplication using Next Generation Sequencing, and Multiplex Ligation Probe Amplification, respectively.

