All results will be shared with patients according to the instructions approved by themselves in the informed consent. A clinical geneticist will discuss results with patients and provide counselling accordingly and will recruit the relatives at risk of inheriting the pathogenic variant with clinical significance. A medical oncologist will explain treatment options if it is appropriate.

Furthermore, genetic counselling will be provided to relatives of patients with germline mutations; we will recommend cancer screening as appropriate.

The study will be conducted at the Instituto Nacional de Ciencias Médicas y Nutrición Salvador Zubirán (INCMNSZ) in Mexico City. Our site is a reference hospital for pancreatic diseases nationwide.

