**Statistical methods:**

This is an observational, cross-sectional study. To estimate the prevalence of *BRCA1* and *BRCA2* germline mutations in unselected pancreatic cancer patients, a sample size of 107 patients is required assuming a prevalence of 7.5%, precision of 5% and 95% Confidence Interval. We use a formula for a prevalence survey, with finite population correction.

*BRCA1* and *BRCA2* prevalence will be defined as the proportion of patients with pathogenic germline mutations in *BRCA1/BRCA2*. Prevalence will be presented as percentage.

Prevalence of other germline mutations will be defined as the proportion of patients with pathogenic germline mutations in genes previously identified as increasing pancreatic cancer susceptibility. Prevalence will be presented as percentage.

Clinical and family history descriptive statistics will be calculated for study variables stratified by BRCA mutation status (positive or negative). The Fisher's exact test will be used to compare the distribution of selected categorical variables between BRCA- positive or negative patients. All statistical tests are two-sided with a statistical significance level of  $P \leq 0.05$ . All statistical analyses will be performed using IBM SPSS Statistics Version 21.

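### Does the exclusion criterion's clock, which stops at presentation to the site, let late-sampled survivors into the study?

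*Combined protocol and SAP*

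**What the plan says.** Three places in the combined protocol and SAP carry the 6-month limit.

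- Study design gives the purpose and the rule: "To decrease potential survivorship bias, we will include only patients with PAC within 6 months of diagnosis".
- Inclusion Criteria, second item: "Diagnosed within the previous 6 months with histologically confirmed pancreatic adenocarcinoma stage I to IV". The date from which the 6 months are counted back is not named.
- Exclusion Criteria, first item: "Diagnosed with pancreatic adenocarcinoma more than 6 months before presenting to the clinical site". Here the end of the interval is named, and it is presentation.

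Study design also sets consecutive recruitment: "Prevalence will be determined by testing all consecutive patients with histologic diagnosis of pancreatic adenocarcinoma (PAC) regardless of family history, clinical stage and treatment". On sampling it says that "10 mL of whole blood mixed with EDTA will be collected from each patient", with no time window relative to diagnosis, presentation or consent. The site is a single national reference hospital.

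Statistical methods gives the planned precision: "a sample size of 107 patients is required assuming a prevalence of 7.5%, precision of 5% and 95% Confidence Interval". It includes no analysis by time since diagnosis.

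**The concern.** Survivorship bias in a prevalence estimate depends on how long a patient must live after diagnosis in order to be sampled. A limit meant to control it should therefore run from diagnosis to enrolment or blood draw. The exclusion criterion runs from diagnosis to presentation. Taken alone, it would not remove a patient who presented within 6 months of diagnosis, or was diagnosed at the site after presenting, and who stayed under care and was sampled a year later.

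The inclusion criterion leaves its reference date unstated, so it could be read in the light of the exclusion criterion, and nothing bounds the time to blood draw. If BRCA1/2 carriers live longer than non-carriers, late sampling enriches the sample for carriers. The primary estimate would then be too high, and so would the figure set against other unselected populations under the Hypothesis heading.

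**Working it through.** **1. The plan's own figure.** With p = 0.075, d = 0.05 and z = 1.96 (Statistical methods), n = z²p(1−p)/d² = 106.6, rounded up to 107. The half-width at n = 107 is 1.96 × √(0.075 × 0.925/107) = 0.0499, or 4.99 points. The stated 107 is reproduced without a finite population correction. The wording of the 6-month limit does not enter this calculation. Expected carriers: 107 × 0.075 = 8.0.

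**2. The eligibility rules side by side.** A patient must meet every inclusion criterion and no exclusion criterion. Take someone who presented at diagnosis and is approached for consent 12 months later.

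| Source | Interval limited | Result |
|---|---|---|
| Study design | diagnosis to inclusion | not eligible |
| Inclusion Criteria, read at the eligibility check | diagnosis to enrolment | not eligible |
| Exclusion Criteria | diagnosis to presentation | not excluded |

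The patient stays out because the first two rules apply whatever the third says. Presentation comes no later than enrolment, so anyone within 6 months of diagnosis at enrolment was also within 6 months at presentation. The exclusion is then redundant, and a redundant exclusion lets nobody in.

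**3. Size under assumptions.** The documents give no survival by carrier status. Assume exponential survival, a non-carrier median of 6 months (h0 = ln 2/6 = 0.1155 per month), a carrier hazard h1 = HR × h0, a true prevalence of 7.5%, and sampling spread uniformly over T months from diagnosis. The relative chance of a carrier being sampled is

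r = [(1 − e^(−h1·T))/h1] / [(1 − e^(−h0·T))/h0],

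and observed prevalence is 0.075r/(0.075r + 0.925).

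For HR 0.7 and T = 6: h1 = 0.0809, r = 4.754/4.328 = 1.098, and observed prevalence is 8.2%.

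| Window T (months) | HR 0.7 | HR 0.5 | HR 1.0 |
|---|---|---|---|
| 2 | 7.7% | 7.9% | 7.5% |
| 6 | 8.2% | 8.7% | 7.5% |
| 12 | 8.8% | 9.8% | 7.5% |
| 24 | 9.6% | 11.5% | 7.5% |

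Only the rows up to 6 months describe the plan. There the shift is 0.7 points (HR 0.7) or 1.2 points (HR 0.5), against a half-width of 4.99 points. The 12- and 24-month rows assume enrolment that Study design forbids.

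**4. Would a sensitivity table help?** Consider prevalence in patients sampled within 2 months of diagnosis against 2 to 6 months. Under HR 0.7 the model gives 7.7% and 8.5%, a difference of 0.8 points. If the 107 patients split about evenly, each group has roughly 4 carriers in 53, with an exact 95% interval of about 2% to 18%. Such a table could neither detect nor rule out a difference of that size.

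**The case for a change.** The best case for a change is that the exclusion criterion is the only item in the two eligibility lists that names where the interval ends. Staff might use it to interpret the undated inclusion criterion and enrol patients already under follow-up. At a national reference hospital taking all stages, treated or not, such patients are plausible. If the inclusion criterion is instead read as counting back from consent, the two criteria use different clocks. Either way the wording is untidy, and correcting it would cost a phrase.

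Part of this stands. The reference dates are inconsistent or unstated, and the interval from enrolment to blood draw has no upper bound. What does not stand is the step to uncontrolled bias. The permissive reading conflicts with the Study design sentence, which limits inclusion and states why. Consecutive recruitment also gives no warrant for drawing on a pool of long-followed patients. Agreement to sample collection is itself an inclusion criterion, so sampling would ordinarily follow enrolment closely, although the document gives no interval.

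It is also true that patients who die before they can be sampled within the 6 months are missed. The plan claims only to decrease this bias. Participants must be alive to consent and give blood, so no rewording of the clock would recover those patients.

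**Conclusion.** The concern does not call for a change. The three statements of the limit do not share one named reference date, which is a missing detail that staff following Study design would fill sensibly: within 6 months of diagnosis at inclusion. On that reading late enrolment is already barred, and the exclusion criterion adds nothing and removes nothing.

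What bias remains within the 6-month window is small beside the planned precision in the illustration, and it is zero if carriers and non-carriers have equal survival. Those figures rest on assumed exponential survival, a 6-month non-carrier median, the hazard ratios shown and uniform sampling, so they indicate scale only. The conclusion on eligibility needs none of them. It rests on reading the inclusion criterion as applying at enrolment and on blood being drawn reasonably soon afterwards.

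The sensitivity table would bring no gain: with about 8 carriers in all, it would alter no conclusion. It would also need diagnosis and sampling dates, whose recording the document does not explicitly specify.

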**Statistical methods:**

This is an observational, cross-sectional study. To estimate the prevalence of *BRCA1* and *BRCA2* germline mutations in unselected pancreatic cancer patients, a sample size of 107 patients is required assuming a prevalence of 7.5%, precision of 5% and 95% Confidence Interval. We use a formula for a prevalence survey, with finite population correction.

*BRCA1* and *BRCA2* prevalence will be defined as the proportion of patients with pathogenic germline mutations in *BRCA1/BRCA2*. Prevalence will be presented as percentage.

Prevalence of other germline mutations will be defined as the proportion of patients with pathogenic germline mutations in genes previously identified as increasing pancreatic cancer susceptibility. Prevalence will be presented as percentage.

Clinical and family history descriptive statistics will be calculated for study variables stratified by BRCA mutation status (positive or negative). The Fisher's exact test will be used to compare the distribution of selected categorical variables between BRCA- positive or negative patients. All statistical tests are two-sided with a statistical significance level of  $P \leq 0.05$ . All statistical analyses will be performed using IBM SPSS Statistics Version 21.

